7.0 REGULATORY AND REPORTING REQUIREMENTS

7.1 Serious Adverse Event Reporting (SAE) for M. D. Anderson-Sponsored IND Protocols

An adverse event or suspected adverse reaction is considered “serious” if, in the view of either the investigator or the sponsor, it results in any of the following outcomes:

- Death
- A life-threatening adverse drug experience – any adverse experience that places the patient, in the view of the initial reporter, at immediate risk of death from the adverse experience as it occurred. It does not include an adverse experience that, had it occurred in a more severe form, might have caused death.
- Inpatient hospitalization or prolongation of existing hospitalization
- A persistent or significant incapacity or substantial disruption of the ability to conduct normal life functions.
- A congenital anomaly/birth defect.

Important medical events that may not result in death, be life-threatening, or require hospitalization may be considered a serious adverse drug experience when, based upon appropriate medical judgment, they may jeopardize the patient or subject and may require medical or surgical intervention to prevent one of the outcomes listed in this definition. Examples of such medical events include allergic bronchospasm requiring intensive treatment in an emergency room or at home, blood dyscrasias or convulsions that do not result in inpatient hospitalization, or the development of drug dependency or drug abuse (21 CFR 312.32).

- Important medical events as defined above, may also be considered serious adverse events. Any important medical event can and should be reported as an SAE if deemed appropriate by the Principal Investigator or the IND Sponsor, IND Office.
- All events occurring during the conduct of a protocol and meeting the definition of a SAE must be reported to the IRB in accordance with the timeframes and procedures outlined in “The University of Texas M. D. Anderson Cancer Center Institutional Review Board Policy for Investigators on Reporting Unanticipated Adverse Events for Drugs and Devices”. Unless stated otherwise in the protocol, all SAEs, expected or unexpected, must be reported to the IND Office, regardless of attribution (within 5 working days of knowledge of the event).
- **All life-threatening or fatal events**, that are unexpected, and related to the study drug, must have a written report submitted within **24 hours** (next working day) of knowledge of the event to the Safety Project Manager in the IND Office.
- Unless otherwise noted, the electronic SAE application (eSAE) will be utilized for safety reporting to the IND Office and MDACC IRB.
- Serious adverse events will be captured from the time of the first protocol-specific intervention, until 30 days after the last dose of drug, unless the participant withdraws consent. Serious adverse events must be followed until clinical recovery is complete and laboratory tests have returned to baseline, progression of the event has stabilized, or there has been acceptable resolution of the event.
- Additionally, any serious adverse events that occur after the 30 day time period that are related to the study treatment must be reported to the IND Office. This may include the development of a secondary malignancy.

Reporting to FDA:

- Serious adverse events will be forwarded to FDA by the IND Sponsor (Safety Project Manager IND Office) according to 21 CFR 312.32.

It is the responsibility of the PI and the research team to ensure serious adverse events are reported according to the Code of Federal Regulations, Good Clinical

Practices, the protocol guidelines, the sponsor's guidelines, and Institutional Review Board policy.

7.2 Expedited reporting by investigator to Incyte and Celgene

Serious adverse events (SAE) are defined above. The investigator will inform Incyte and/or Celgene of any SAE within 24 hours of being aware of the event via email and/or fax. Respective companies will be informed based on the attribution of a given SAE:

1. Due to INCB018424 alone – These SAEs will only be reported to INCYTE.
2. Due to the Lenalidomide – These SAEs will only be reported to CELGENE.
3. Due to both the INDB018424 and the Lenalidomide – These SAEs will be reported to INCYTE and CELGENE.
4. All pregnancies will be reported to both companies.

If the investigator can't associate causality with one or the other alone then causality needs to be associated with the combination of the products. These SAEs will go to both INCYTE and CELGENE.

Adverse events will be documented in the medical record and entered into the case report form. PDMS/ CORE will be used as the electronic case report form for this protocol. Investigator or physician designee is responsible for verifying and providing source documentation for all adverse events and assigning the attribution for each event for all subjects enrolled on the trial. SAEs must be documented on MDACC "Internal SAE Report Form for Prompt Reporting". This form must be completed and supplied to Incyte and/or Celgene within 24 hours/1 business day at the latest on the following working day. The initial report must be as complete as possible, including details of the current illness and (serious) adverse event, and an assessment of the causal relationship between the event and the investigational product(s). Information not available at the time of the initial report (e.g., an end date for the adverse event or laboratory values received after the report) must be documented on a follow-up MDACC SAE reporting form.

Pregnancies and suspected pregnancies (including a positive pregnancy test regardless of age or disease state) of a female subject or the female partner of a male subject occurring while the subject is on study drug, or within 60 days of the subject's last dose of study drug, are considered immediately reportable events. Study drug is to be discontinued immediately in a female patient and the patient instructed to return any unused portion of the study drug to the investigator(s). The pregnancy, suspected pregnancy, or positive pregnancy test must be reported to Incyte and Celgene immediately by phone and facsimile using the MDACC AE report form. The female should be referred to an obstetrician-gynecologist experienced in reproductive toxicity for further evaluation and counseling.

The Investigator(s) will follow the female subject until completion of the pregnancy, and must notify Incyte and Celgene of the outcome of the pregnancy as a follow-up to the initial AE report. If the outcome of the pregnancy meets the criteria for immediate classification as a SAE (i.e., spontaneous or therapeutic abortion [any congenital anomaly detected in an aborted fetus is to be documented], stillbirth, neonatal death, or congenital anomaly [including that in an aborted fetus]), the Investigator(s) should follow the procedures for reporting SAEs (i.e., report the event to Incyte and Celgene within 24 hours of the Investigator's knowledge of the event). In the case of a live "normal" birth, Incyte and Celgene should be advised within 24 hours of the Investigator's knowledge of the event. All neonatal deaths that occur within 30 days of birth should be reported, without regard to causality, as SAEs. In addition, any infant death after 30 days that the Investigator(s) suspects is related to the in utero exposure to the study drug should also be reported to Incyte and Celgene within 24 hours of the Investigators' knowledge of the event. If the female is found not to be pregnant, any determination regarding the subject's continued participation in the study will be determined by the principal investigator.

8.0 STATISTICAL CONSIDERATIONS

All subjects meeting the eligibility criteria that have signed a consent form and have begun treatment will be evaluable for response. This is a two stage, phase II trial designed to assess the effect of therapy in subjects with Primary, Post Polycythemia Vera, or Post Essential Thrombocythemia Myelofibrosis (PMF, post-PV MF, or post-ET MF). Secondary objective is to determine the safety of therapy in this population.

The primary objective of this study is to assess efficacy in terms of the objective response rate (complete and partial response, and clinical improvement by IWG-MRT) in patients with MF. The Min-Max two-stage design proposed by Simon will be implemented. Sample size and decision criteria are chosen to reduce the expected accrual if the treatment is ineffective in regard to response relative to having no interim stopping rule. The target response rate is 50%. A response rate of 35% or less will be considered unacceptable and treatment with the therapy will be discontinued. Given the response rates stated above, if the probability of inappropriately accepting a poor therapy is 10% ($\alpha=0.1$), a total sample size of 49 patients will result in 80% power ($\beta=0.2$).

In the first stage of the design, a total of 31 patients will be enrolled and the study will be put on hold to assess response. If 10 or fewer patients respond to the combination therapy, after being treated for 6 months or discontinued due to excessive toxicity or lack of efficacy, then the study will be terminated and the therapy will be declared ineffective. Those patients who stopped receiving one of the two study drugs due to safety reasons will be counted as failures in the efficacy analysis. However, if 11 or more patients respond, up to an additional 18 patients will be enrolled to complete the study.

After a total of 49 patients have been enrolled into the study, if 21 or fewer patients respond to the therapy, the therapy will be declared ineffective. However, if greater than 21 patients respond to the therapy, the therapy will be considered efficacious. The probability of early termination due to unacceptable response rate is 46% under the null hypothesis.

Data from all subjects who receive any study drug will be included in the safety analyses. Subjects who entered the study and did not take any of the study drug and had this confirmed, will not be evaluated for safety.

The severity of the toxicities will be graded according to the NCI CTCAE v4.0 whenever possible. We will follow standard reporting guidelines for adverse events (Appendix C; Leukemia-specific Adverse Event Recording and Reporting Guidelines).

Descriptive statistics will be utilized to assess time to response and response duration.

Duration of response: duration of response is defined as the date at which the subject's objective status is first noted to be a CR, PR or CI to the date progression (no longer meeting criteria for either CR, PR or CI) is documented (if one has occurred). Patients who continue to respond as of the data cut-off date will be censored as of the date of their last assessment documenting continued response.

Time to response: The time to response is defined as the time from study registration to the first date at which the subject's objective status was classified as a response (CR, PR or CI). In subjects who do not achieve a response, time to response will be censored at the subject's last evaluation date. The distribution for each of these event-time variables (duration of response and time to response) will be estimated by Kaplan-Meier curves.

Anemia: Descriptive statistics will be used to explore improvements in anemia and transfusion dependence. The following outcomes will be summarized: mean changes in hemoglobin at monthly intervals. The proportion of transfusion independent patients not requiring transfusions on study who experience an increase of 2 g/dL in their hemoglobin relative to baseline, the proportion of transfusion dependent patients (defined as requiring a transfusion of 2 units PRBCs monthly for 3 months (12 weeks) prior to starting the trial) who become transfusion independent (not requiring a transfusion of PRBCs over a period of 3 months (12 weeks) while on study), the proportion of transfusion dependent patients who become transfusion independent and have a 1 g/dL increase in hemoglobin relative to baseline, and the proportion of transfusion independent patients requiring a transfusion while on study.

JAK2V617F Allele burden: Change in JAK2V617 allele burden from baseline to each visit where it is measured.

This phase II clinical trial will have a stopping rule based on toxicity defined as an adverse events considered to be at least possibly related to treatment. In particular, accrual to the study will be temporarily suspended if: a) 2 or more among the first 10 subjects treated on this trial experiences a Grade 4 non-hematologic toxicity or a

serious adverse event that is felt to be drug related. b) 20% or more of subjects (when more than 10 subjects have been accrued) experience a Grade 4 non-hematologic toxicity or serious adverse event that is felt to be drug related. After consideration by the study team (study chair, statistician), a decision will be made as to whether accrual can resumed after approval of the appropriate IRB.

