1.0 HYPOTHESIS AND OBJECTIVES

Hypothesis

Ruxolitinib (also known as INCB018424), a JAK1/2 inhibitor, and lenalidomide (immunomodulatory inhibitory drug; IMiD) are effective and tolerable treatments for patients with myelofibrosis (MF). Combination of these agents in patients with MF can improve the overall clinical response to therapy without causing excessive toxicity.

Objectives

Primary:

- to determine the efficacy of the combination of INCB018424 with lenalidomide in patients with MF, in achieving objective improvements in disease status

Secondary:

- to determine the safety of the combination in patients with MF

Exploratory:

- to explore time to response and duration of response
- to explore the effect of the combination on anemia and transfusion dependence in patients with MF
- to explore changes in JAK2V617F allele burden

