Clinical Experience

We conducted a phase 1–2 trial of INCB018424 in patients with *JAK2* V617F–positive or *JAK2* V617F–negative primary myelofibrosis, post–essential thrombocythemia myelofibrosis, or post–polycythemia vera myelofibrosis. A total of 153 patients received INCB018424 for a median duration of more than 14.7 months. The initial dose-escalation phase established 25 mg twice daily or 100 mg once daily as maximum tolerated doses, on the basis of reversible thrombocytopenia. A dose-dependent suppression of phosphorylated signal transducer and activator of transcription 3 (STAT3), a marker of JAK signaling, was demonstrated in patients with wild-type *JAK2* and in patients with the *JAK2* V617F mutation. We studied additional doses and established that a 15-mg twice-daily starting dose, followed by individualized dose titration, was the most effective and safest dosing regimen. At this dose, 17 of 33 patients (52%) had a rapid objective response ($\geq 50\%$ reduction of splenomegaly) lasting for 12 months or more, and this therapy was associated with grade 3 or grade 4 adverse events (mainly myelosuppression) in less than 10% of patients. Patients with debilitating symptoms, including weight loss, fatigue, night sweats, and pruritus, had rapid improvement. Clinical benefits were associated with a marked diminution of levels of circulating inflammatory cytokines that are commonly elevated in myelofibrosis.

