2.3 Lenalidomide

Lenalidomide is the lead compound in a proprietary class of Celgene compounds known as IMiDs® with immunomodulatory and anti-angiogenic properties that could confer antitumor and antimetastatic effects. It is a derivative of thalidomide, combining higher efficacy and lower toxicity than its parent compound. Lenalidomide has been demonstrated to possess anti-angiogenic activity through inhibition of bFGF, VEGF and TNF-alpha induced endothelial cell migration, due at least in part to inhibition of Akt phosphorylation response to bFGF. In addition, lenalidomide has a variety of immunomodulatory effects. Lenalidomide stimulates T cell proliferation, and the production of IL-2, IL-10 and IFN-gamma, inhibits IL-1 beta and IL-6 and modulates IL-12 production.

Clinical experience in myelofibrosis with lenalidomide

Two similarly designed but separate phase 2 studies involving single-agent lenalidomide in a total of 68 patients with symptomatic myelofibrosis were reported in one paper. Protocol treatment consisted of oral lenalidomide at 10 mg/d (5 mg/d if baseline platelet count < 100 x 10⁹/L) for 3 to 4 months with a plan to continue treatment for either 3 or 24 additional months, in case of response. Overall response rates were 22% for anemia, 33% for splenomegaly, and 50% for thrombocytopenia. Response in anemia was deemed impressive in 8 patients whose hemoglobin level normalized from a baseline of either transfusion dependency or hemoglobin level lower than 100 g/L. Additional treatment effects in these patients included resolution of leukoerythroblastosis (4 patients), a decrease in medullary fibrosis and angiogenesis (2 patients), and del(5)(q13q33) cytogenetic remission accompanied by a reduction in JAK2(V617F) mutation burden (1 patient). Grade 3 or 4 adverse events included neutropenia (31%) and thrombocytopenia (19%). Authors concluded that lenalidomide engenders an intriguing treatment activity in a subset of patients with MF that includes an unprecedented effect on peripheral blood and bone marrow abnormalities.

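### Does testing the combination only against 35% undermine the efficacy conclusion, given a cited 52% for ruxolitinib alone?

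*Combined protocol and SAP*

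**What the plan says.** Section 8.0 (Statistical Considerations) uses a Simon minimax two-stage design for the proportion with complete remission, partial remission or clinical improvement: "The target response rate is 50%. A response rate of 35% or less will be considered unacceptable". The first stage enrols 31 patients and stops if 10 or fewer respond. Otherwise 18 more are enrolled. At 49 patients, 21 or fewer responses means ineffective. "However, if greater than 21 patients respond to the therapy, the therapy will be considered efficacious". The same section adds: "Those patients who stopped receiving one of the two study drugs due to safety reasons will be counted as failures in the efficacy analysis".

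The hypothesis in Section 1.0 is worded as an improvement: "Combination of these agents in patients with MF can improve the overall clinical response to therapy without causing excessive toxicity". It names no comparator. The primary objective, in Section 1.0 and again in Section 8.0, is to assess how effective the combination is, with no reference treatment.

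Section 2.2 reports earlier experience with ruxolitinib alone at "a 15-mg twice-daily starting dose, followed by individualized dose titration": "17 of 33 patients (52%) had a rapid objective response", which that section defines as at least a 50% "reduction of splenomegaly) lasting for 12 months or more". Section 5.0 plans the same starting dose. For lenalidomide alone, Section 2.3 reports: "Overall response rates were 22% for anemia, 33% for splenomegaly, and 50% for thrombocytopenia". It also gives an overall IWG-MRT response of 12/40 (30%) for lenalidomide plus prednisone.

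**The concern.** If the hypothesis is read as improvement over the component drugs, the natural reading, the benchmark looks too low. The smallest passing result is 22/49 = 44.9% and the target is 50%. Both are below the 17/33 = 51.5% that the protocol quotes for ruxolitinib alone. The 10% error rate guards against a combination whose true rate is 35% or less. It does not guard against a combination that is no better than its ruxolitinib component. A reader could then take a positive result as evidence that adding lenalidomide helps when the trial has not shown that. Prednisone is added for non-responders after three cycles (Section 5.0), so some counted responses may owe something to a third drug, which makes attribution harder still.

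**Working it through.** **Inputs.** From Section 8.0: p0 = 0.35, p1 = 0.50, n1 = 31, r1 = 10, n = 49, r = 21, alpha = 0.10, power = 0.80. From Section 2.2: 17/33. From Section 2.3: 12/40 = 30%, and 33% for spleen response on lenalidomide alone.

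**Step 1: reproduce the design.** With X1 ~ Bin(31, p) and X2 ~ Bin(18, p),

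- P(stop early) = P(X1 ≤ 10)
- P(pass) = Σ over x = 11 to 31 of P(X1 = x) · P(X2 ≥ 22 − x)

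At p = 0.35, P(stop early) = 0.455 (stated 46%) and P(pass) = 0.0966 (limit 0.10). At p = 0.50, P(pass) = 0.801 (stated 80%). Expected sample size at 35% is 31 + (1 − 0.455) × 18 = 40.8. A search for the smallest total sample size meeting both error limits returns 10/31 and 21/49. The plan's figures are right for its inputs.

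**Step 2: what the smallest pass shows.** 22/49 = 44.9%. The exact 80% interval, which matches a one-sided 10% level, is 35.1% to 55.0%. A pass therefore supports a rate above 35% at the level the plan chose. The exact 90% interval, 32.7% to 57.6%, includes 35%, so the claim holds at that level and no stricter one.

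**Step 3: the rule if lenalidomide added nothing.** The true rate would then equal the ruxolitinib-alone rate on this trial's endpoint, which the documents do not give. Assumed values:

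| Assumed true rate | P(pass) |
|---|---|
| 30% (cited for lenalidomide plus prednisone) | 1.9% |
| 33.5% (lower 95% limit of 17/33) | 6.4% |
| 35% | 9.7% |
| 40% | 28.5% |
| 45% | 55.7% |
| 50% | 80.1% |
| 51.5% (17/33) | 85.5% |
| 69.2% (upper 95% limit of 17/33) | over 99% |

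**Step 4: can 52% be carried over?** Set the two endpoints side by side.

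- *Cited study (Section 2.2):* spleen reduction of at least 50%, lasting 12 months or more, with no baseline spleen size stated.
- *This trial (Sections 6.0 and 8.0):* complete or partial remission or clinical improvement. Clinical improvement can come from hemoglobin or transfusion status, platelets, neutrophils or spleen, and is validated at 8 weeks. The spleen criterion needs a baseline of at least 10 cm for a 50% reduction, or more than 5 cm for a spleen that becomes non-palpable.
- *Entry and scoring:* splenomegaly is not an entry requirement, and stopping one drug for safety counts as failure.

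The extra routes to response and the shorter duration would tend to raise the rate here. The spleen-size thresholds, entry without splenomegaly and the failure rule would tend to lower it. The net direction cannot be settled from the documents. In addition, 17/33 has an exact 95% interval of 33.5% to 69.2%, which contains 35%.

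**The case for a change.** The strongest argument for acting is that the hypothesis speaks of improvement, both drugs are introduced as already effective, and Section 8.0 neither gives a source for 35% nor says that a pass leaves the comparison with ruxolitinib open. One sentence of caution would cost nothing, and a descriptive spleen summary could come from measurements already scheduled. Passing results of 22 to 25 responses (44.9% to 51.0%) all lie below 17/33, and at a true 50% they make up 0.414 of the 0.801 chance of passing, about half.

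What stands is that a pass is not evidence of superiority to ruxolitinib alone, and the reasoning behind 35% is not written down.

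The rest does not carry a change. Counts of 22 to 25 are ordinary sampling spread around the 49 × 0.50 = 24.5 responses expected at the target. Even at a true 17/33 they account for 0.384/0.855 = 45% of passes. Judging them against 17/33 is also the cross-endpoint comparison that Step 4 rules out. A sentence of caution would apply to any single-arm trial and would alter no result. A spleen summary could not reproduce the cited definition, would have coarse 12-month timing because the spleen is measured only every 3 to 6 cycles after cycle 3, and would invite the informal comparison it is meant to avoid. Section 8.0 already plans Kaplan-Meier summaries of time to response and response duration.

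**Conclusion.** No change to the plan is needed. The rule answers the non-comparative primary objective, and its meaning can be read from Section 8.0: activity above 35% at the one-sided 10% level. That reference is not arbitrary against the protocol's own background. It lies above the 30% overall response cited for lenalidomide plus prednisone, where the rule would pass only 1.9% of the time, and above the 33% spleen response for lenalidomide alone. A pass therefore bears on part of the improvement hypothesis. The part it leaves open is ruxolitinib alone. A single-arm trial of 49 patients is a fair phase II trade-off for an activity screen and is not built to settle that question.

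The size of the concern cannot be fixed. Under no added benefit the chance of a pass is 6% to over 99% across the 95% interval of 17/33, and even that assumes the rate transfers between endpoints. This conclusion rests on reading *efficacious* as Section 8.0 defines it. A report claiming superiority to ruxolitinib from this result would go beyond the plan. An interpretive sentence to that effect would be optional.

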5.0 TREATMENT PLAN

Four weeks on therapy is considered one cycle of therapy. INCB018424 and lenalidamide will be given orally in an outpatient setting. INCB018424 will be given continuously daily in 28-day cycles, and lenalidamide will be given on days 1-21 of 28 day cycles. Dosage for cycles can be reduced, increased or delayed based assessment of efficacy and on adverse events, if any occur, as described below. Delays of a maximum of 8 weeks are allowed from scheduled next cycle.

Subjects will be asked to maintain a diary to record drug administration. Subjects will be asked to bring any unused study drug to the research center at their next visit. Research personnel will count and record the number of used and unused study drug capsules/tablets (both ruxolitinib and lenalidomide) at each visit and reconcile with the subject diary. The study coordinator will question the patient regarding adherence to the dosing regimen, record the number of capsules/tablets and strengths returned in the carton, the date returned and determine treatment compliance before dispensing new medication to the study patient. Compliance below 80% will require counseling of the patient by study site personnel.

The planned dose and schedule of investigation of INCB018424 is 15 mg orally twice daily (BID), continuously in 28-day cycles. Lenalidomide will be taken orally 5 mg/day in the morning each day on days 1-21, followed by 7 days of no therapy of each 28-day cycle; medication will be mailed to participants, per the RevAssist® Program.

Twenty eight days is considered one cycle of therapy. Attempts will be made to provide an adequate treatment period of at least 6 months unless significant toxicity observed, to account for delayed time to response observed with biologic agents. Responders will continue therapy for 6 years unless progression of disease or toxicity warranting discontinuation of therapy is observed.

Prednisone will be added for patients who have not responded after 3 cycles of therapy. It will be dosed orally at the dose of 30 mg/day during cycle 4, 15 mg/day during cycle 5, and 15 mg every other day during cycle 6, and then it will be discontinued.

All patients will be registered in the Clinical Oncology Research system(CORE) at MD Anderson Cancer Center after the informed consent is signed.

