6.0 CRITERIA FOR RESPONSE

Best overall response will be categorized according to the International Working Group Criteria:

Complete remission (CR): Requires all of the following in the absence of both transfusion and growth factor support;

- Complete resolution of disease-related symptoms and signs including palpable hepatosplenomegaly.
- Peripheral blood count remission defined as hemoglobin > 11 g/dL, platelet count $\geq 100 \times 10^9/L$, and absolute neutrophil count $\geq 1.0 \times 10^9/L$.
- Normal leukocyte differential including disappearance of nucleated red blood cells and immature myeloid cells in the peripheral smear, in the absence of splenectomy.*
- Bone marrow histological remission defined as the presence of age-adjusted normocellularity, < 5% myeloblasts, and an osteomyelofibrosis grade of ≤ 1 .**

Partial remission (PR): Requires all of the above criteria for CR except the requirement for bone marrow histological remission. However, a repeat bone marrow biopsy is required in the assessment of PR and may or may not show favorable changes that do not however fulfill criteria for CR.

Clinical improvement (CI): Requires one of the following in the absence of both disease progression (as outlined below) and CR/PR assignment (*CI response is validated only if it lasts for ≥ 8 weeks*).

- A ≥ 2 g/dL increase in hemoglobin level or becoming transfusion independent (applicable only for patients with baseline hemoglobin level of < 10 g/dL).[§]
- Either a $\geq 50\%$ reduction in palpable splenomegaly of a spleen that is ≥ 10 cm at baseline or a spleen that is palpable at > 5 cm at baseline becomes not palpable.^{§§}
- A $\geq 100\%$ increase in platelet count and an absolute platelet count of $\geq 50,000 \times 10^9/L$. (applicable only for patients with baseline platelet count of < $50 \times 10^9/L$).
- A $\geq 100\%$ increase in ANC and an ANC of $\geq 0.5 \times 10^9/L$ (applicable only for patients with baseline absolute neutrophil count of < $1 \times 10^9/L$).

Progressive disease: Requires one of the following:[¶]

- Progressive splenomegaly that is defined by the appearance of a previously absent splenomegaly that is palpable at > 5 cm below the left costal margin or a $\geq 100\%$ increase in palpable distance for baseline splenomegaly of 5-10 cm or a $\geq 50\%$ increase in palpable distance for baseline splenomegaly of > 10 cm.
- Leukemic transformation confirmed by a bone marrow blast count of $\geq 20\%$.

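### The 10/31 and 21/49 rules test ruxolitinib plus lenalidomide with prednisone added for non-responders, not the two-drug combination named in the primary objective

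*Combined protocol and SAP*

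**What the plan says.** **Objective.** Section 1.0 gives the primary aim as "to determine the efficacy of the combination of INCB018424 with lenalidomide in patients with MF". Prednisone is not named there.

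**Treatment.** Section 5.0 states: "Prednisone will be added for patients who have not responded after 3 cycles of therapy". The schedule is "30 mg/day during cycle 4, 15 mg/day during cycle 5, and 15 mg every other day during cycle 6", after which it stops. This is the planned path for every early non-responder, not an occasional rescue.

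**Decision rule.** Section 8.0 uses a Simon minimax design. On the rates it says "The target response rate is 50%. A response rate of 35% or less will be considered unacceptable". The stage 1 rule begins "If 10 or fewer patients respond to the combination therapy, after being treated for 6 months", and the trial then ends for lack of efficacy. At 49 patients, "if greater than 21 patients respond to the therapy, the therapy will be considered efficacious". The six-month period appears only in the stage 1 sentence.

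**Counting.** Section 8.0 has one rule on a change of drugs: "Those patients who stopped receiving one of the two study drugs due to safety reasons will be counted as failures in the efficacy analysis". Section 6.0 classifies best overall response, with no cut at the start of prednisone. On clinical improvement (CI) it adds "CI response is validated only if it lasts for" at least 8 weeks. Neither section mentions prednisone. Section 5.1 says only that changing or stopping prednisone does not take a patient off study.

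**The concern.** The objective and the wording of Section 8.0 speak of two drugs. A patient who fails on those two drugs for 12 weeks, starts prednisone and then responds is nevertheless a responder under the rule, and the response is credited to the two-drug combination.

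A combination no better than the unacceptable 35% could therefore pass stage 1 and the final rule with help from prednisone, and be reported as efficacious. There is no control arm, and no planned summary separates the two sources of response, so a reader of the results could not tell which regimen earned the verdict.

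**Working it through.** **1. Reproduce the design.** Inputs from Section 8.0: stop at 10 or fewer of 31; success at 22 or more of 49 (18 patients in stage 2); rates 35% and 50%. With X1 ~ Bin(31, p) and X2 ~ Bin(18, p):

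- P(stop at stage 1) = P(X1 ≤ 10)
- P(efficacious) = sum over x ≥ 11 of P(X1 = x) · P(X2 ≥ 22 − x)

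At p = 0.35, P(stop) = 0.455 and P(efficacious) = 0.097. At p = 0.50, P(efficacious) = 0.801. These match the stated 46%, 10% and 80%. A search over designs confirms that 49 is the minimum total. The arithmetic of the plan is sound.

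**2. Place prednisone in the window.** Cycles last 28 days. Three cycles end on day 3 × 28 = 84 (week 12). Cycles 4 to 6 are days 85 to 168, within six months.

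**3. Let prednisone contribute.** Let p2 be the true two-drug response rate over the window. Let x be the share of the remaining patients who respond once prednisone is added. The counted rate is

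p = p2 + (1 − p2) · x.

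The documents do not give x. It is an assumption, shown as a range.

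With p2 = 0.35, the unacceptable rate:

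| x | counted rate | P(stop at stage 1) | P(efficacious) |
|---|---|---|---|
| 0 | 0.350 | 0.455 | 0.097 |
| 5% | 0.35 + 0.65 × 0.05 = 0.3825 | 0.312 | 0.206 |
| 10% | 0.35 + 0.65 × 0.10 = 0.415 | 0.195 | 0.362 |
| 15% | 0.35 + 0.65 × 0.15 = 0.4475 | 0.111 | 0.543 |

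With p2 = 0.30, P(efficacious) is 0.019 at x = 0 and 0.158 at x = 10% (counted rate 0.30 + 0.70 × 0.10 = 0.37).

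**4. Is x near 10% plausible?** Section 2.3 allows only a weak comparison across separate, non-randomised studies. Response to lenalidomide alone was 22% for anemia and 33% for spleen; with prednisone it was 30% and 42%. If the whole difference were due to prednisone:

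- anemia: (0.30 − 0.22)/(1 − 0.22) = 0.08/0.78 = 10%
- spleen: (0.42 − 0.33)/(1 − 0.33) = 0.09/0.67 = 13%

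Neither study included ruxolitinib, and in the second prednisone began in cycle 1 in patients not selected for non-response.

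**5. In counts.** With 17 two-drug responders of 49 (34.7%), 32 patients remain. Five conversions (5/32 = 16%) give 22, which is a declaration of efficacy.

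**6. Timing.** A CI first seen after week 12 − 8 = 4 has not lasted 8 weeks by the end of cycle 3. Section 5.0 does not say whether that patient has responded when prednisone is due. After cycle 3, Section 5.6 and Appendix I assess response every 3 to 6 cycles, so the next required assessment falls at cycle 6 or as late as cycle 9. A response that starts in cycles 4 to 6 may be dated well after it began.

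**The case against.** The strongest reply is that the plan is clear enough and its error rate correct. All eligible, consented, treated patients are evaluable; best overall response has no cut at prednisone; Section 5.0 asks for at least six months of treatment because responses may be late; and the only change of drugs that makes a patient a failure is stopping one of the two study drugs for safety. Prednisone is a protocol step with its own entry in Section 3.3 and its own exclusion criterion. On this view the trial tests a strategy, and the 9.7% error belongs to that strategy.

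Most of this stands, and it limits the point in three ways.

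- A reader might infer that Section 8.0 leaves two equally open counts, so that the verdict could be chosen once the data are seen. The documents do not support that: Sections 6.0 and 8.0 favour counting responses after prednisone starts, and nothing supports excluding them.
- A reader might infer that the 10% error is wrong. It is not wrong for the regimen given.
- A reader might push x to 20% or 30%, where the chance of a positive verdict at a two-drug rate of 35% is 71% or 93%. Those values have little support. Thirty percent equals the whole response rate in the cited lenalidomide-prednisone study.

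The reply does not remove the mismatch. If the strategy is what is tested, the objective and the conclusion must name it, and at present they name two drugs.

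**Conclusion.** The concern holds as a mismatch between the stated objective and the regimen that the rule tests. The design figures are correct for ruxolitinib plus lenalidomide with prednisone added for non-responders. They give no 10% error protection to a claim about the two drugs alone.

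The size depends on an unknown conversion rate. At a true two-drug rate of 35%, the chance of a positive verdict rises from 10% to 21%, 36% or 54% for x of 5%, 10% or 15%, and stage 1 stopping falls from 46% to 20% at x = 10%. These figures assume independent patients, a common x, and that responses after prednisone starts count. The rough comparison in Section 2.3 points to about 10% to 13%, but it is too weak to fix a value.

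This should be corrected. It takes no view on whether prednisone should be given, or on whether 35% is the right threshold.

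**What to change.** Keep 49 patients, both cut-offs and the treatment plan.

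1. In Section 8.0, state that a response within the assessment window counts whether or not prednisone was started, and that 22 or more of 49 supports a response rate above 35% for ruxolitinib plus lenalidomide with prednisone added for non-responders. Word the objective and the conclusion to match. Make no two-drug efficacy claim from this rule alone.
2. Report descriptively the number of responses first documented before the first prednisone dose, out of 49, with an exact 80% confidence interval (for scale, 22/49 gives 35.1% to 55.0%), and the number first documented after it. Do not make the first count a second pass/fail gate. It would apply thresholds set for six months to response by about week 12, and at a true 50% its power would be 56% or 29% if 10% or 20% of responses (assumed shares) came later.
3. Apply the stage 1 window to the final rule. Reconcile Sections 5.0, 5.6 and 6.0 on the status of a CI that has not yet lasted 8 weeks at the end of cycle 3, and on how responses are dated when assessments after cycle 3 are 3 to 6 cycles apart.

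The cost is a few sentences, the first prednisone date in the case report form, one extra count and a narrower headline conclusion. The pre-prednisone count will understate two-drug efficacy if some two-drug responses come after week 12. That is possible: the cited lenalidomide-prednisone study had a median time to response of 12 weeks, range 2 to 32.
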